11.2 Adverse Events

Adverse events will be coded to the Preferred Term (PT) level using the Medical Dictionary for Regulatory Affairs (MedDRA dictionary), version 23.0 or higher. Treatment-emergent AEs (TEAEs) are defined as AEs reported at or after the start of the first infusion. All AEs regardless of when they were reported will be listed.

Summaries of TEAEs will count the number of subjects, not the number of events, that is, subjects with multiple occurrences of the same TEAE will be counted once.

The number and percentage of subjects with TEAEs will be reported. Also, the number and percentage of subjects with serious TEAEs, TEAEs by severity, and serious TEAEs related to investigational product will be presented. Adverse events will be presented for Treatment Period 1 and RiS Analysis Set. For Treatment Period 2 summaries will be presented for the RWS Analysis Set. In addition, the summaries will be given for C1-INH over the whole study for RWS Analysis Set and a summary across the whole study will be given for the RiS Analysis Set.

A summary of number and percentage of subjects with any TEAE by maximum severity or grade will be produced. TEAEs will be sorted by System Organ Class (SOC) and PT in descending order of incidence overall treatment arms. The summary will report the number of subjects with at least one TEAE, counted for the maximum severity and, for each PT reported, the number of subjects for each, counted for the maximum severity.

In addition, the frequency and percentage of TEAEs will be summarized and displayed in two ways: 1) in descending order of incidence in whole study for RiS Analysis Set by PT only and 2) in descending order of incidence whole study for RiS Analysis Set by SOC and PT. In the SOC row, the number of subjects with multiple events under the same system organ class will be counted once.

A separate summary will be provided for study treatment-related serious TEAEs. Missing relationship to study treatment will be imputed as described in [Section 8.1.2](#); this summary will also include the number and percentage of TEAEs with a missing relationship to aid in interpretation of the results.

By-subject listings will also be provided with detailed information to support the different AE summaries.

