4.2.2.2 Secondary Endpoints

Table 2 Secondary Endpoints

[figure not shown]
Secondary Objective	Endpoints	Summary Measure
1	All-cause allograft failure through the Responder Follow-up Period	Proportion of subjects with all-cause allograft failure through the Responder Follow-up Period (ie, within 48 months after enrollment). Allograft failure is defined as 1 of the following: 
• Allograft nephrectomy, institution of permanent dialysis, or return to the transplant waitlist for renal transplant, whichever occurs first, OR• Subject death by any cause.
1	Change in eGFR from baseline to TP1	The difference between the End-of-TP1 eGFR and baseline eGFR.
1	Change in eGFR from TP1 to the End-of -TP2.	The difference between the End-of-TP2 eGFR and the End-of-TP1 eGFR.
1	The rate of change of eGFR.	The rate of change of eGFR during TP2 as defined by the slope of the mean regression of eGFR over time in TP2.
1	Time (weeks) to all-cause allograft failure through the Responder Follow-up Period	Time (weeks) to all-cause allograft failure through the Responder Follow-up Period (ie, within 48 months after enrollment).

Secondary Objective	Endpoints	Summary Measure
1	Responder status at the End-of-TP1.	Proportion of responders at the End-of-TP1. Response is defined as End-of-TP1 eGFR that is ≥ 20 mL/min/1.73 m ² and $\geq 90\%$ of the baseline eGFR.
1	Subject death through the Responder Follow-up Period.	Proportion of subjects surviving through the Responder Follow-up Period.
2	Any AE assessed as related to investigational product during TP1 and during TP2.	Proportion of subjects with any AE assessed as related to investigational product.
3	Pre-dose C1-esterase inhibitor functional activity at Day 1, Week 12, and Week 38.	Mean pre-dose C1-esterase inhibitor functional activity at Day 1, Week 12, and Week 38.
3	For the subset of subjects with sequential PK sampling, C1-esterase inhibitor functional activity C _{max} , and AUC _{0-t} after IV and/or SC administration of C1-INH.	C1-esterase inhibitor functional activity C _{max} and AUC _{0-t} for IV and SC administration.

AE = adverse event; AUC_{0-t} = area under the plasma-concentration time curve 0 to a definite time; C_{max} = maximum concentration; eGFR = estimated glomerular filtration rate; IV = intravenous; PK = pharmacokinetic; SC = subcutaneous; TP1 = Treatment Period 1; TP2 = Treatment Period 2

[figure not shown]

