4.6 Planned Interim Analyses and Reviews

The study will be monitored by an Independent Data Monitoring Committee (IDMC). The meeting frequency, specific responsibilities, and composition of the IDMC will be outlined in a separate document, the IDMC charter.

The study was terminated by the sponsor on 15 September 2020, therefore, no interim analysis will be conducted.

5 Changes in the Conduct of Planned Analyses

There are changes in the planned analyses (from those specified in the protocol) following the sponsor's decision to terminate the study. There will be no analysis of the endpoints below. Data from these endpoints will be presented only in subject listings.:.

- Secondary endpoint of proportion of subjects with all-cause allograft failure through the Responder Follow-up Period,
- Time to all-cause allograft failure through 48 months after enrollment,
- Change in eGFR from End-of-TP1 to the End-of-TP2,
- Rate of change of eGFR in Treatment Period 2,
- CCI [REDACTED],
- Plasmapheresis sessions,
- CCI [REDACTED]
[REDACTED],
- CCI [REDACTED]
[REDACTED],
- CCI [REDACTED]
[REDACTED],
- Trough IVIg concentrations at designated time points,
- CCI [REDACTED],

For other endpoints the statistical analysis was reduced as described in the sections of this SAP.

6 Study Analysis Sets

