8.1.1 Imputation of Non-Date Missing Data

Non-date Clinical Data

All available data will be analyzed using suitable statistical methods. For analysis of percent responders, all subjects in the appropriate analysis set (ITT Analysis Set or mITT Analysis Set) will be included in the denominator when calculating the percentages; any subject who drops out of the study at any time after randomization will be defined for the purpose of analysis as a non-responder.

Subjects with the designation of treatment relationship for adverse events (AEs) and serious adverse events (SAEs) missing will have the worst case assumed to impute the relationship: if relationship to study treatment is missing it will be assumed to be “Yes”.

In summaries of absolute values and change from baseline, subjects with missing baseline values will not be included in baseline rows or in the change from baseline summary statistics.

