11.4 Deaths and Serious Adverse Events

A by-listing will be generated to provide subject-specific details on subjects who died.

The following summaries will be provided for Treatment Period 2 and the RWS Analysis Set. In addition, a summary for C1-INH over the whole study for RWS Analysis Set and a summary across the whole study will be given for the RiS Analysis Set:

- Serious TEAEs,

- Serious TEAEs related to Study Treatment.

The following listings will be provided for RiS Analysis Set:

- Serious Non-TEAEs,
- Serious TEAEs,
- TEAEs resulting in death.

11.5 Adverse Events Leading to Discontinuation of Study Treatment, Withdrawal from the Study, and Other Significant Adverse Events

The following listings will be provided based on RiS Analysis Set:

- TEAEs Leading to Discontinuation of Study Treatment,
- Non-TEAEs leading to Withdrawal from the Study,
- TEAEs leading to Withdrawal from the Study.

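### The SAP tabulates relationship to study product for serious events only, so its one safety secondary endpoint has no planned output; its treatment-emergent windows also conflict

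*SAP*

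**What the plan says.** **The endpoint.** SAP Table 2 (4.2.2.2) lists "Any AE assessed as related to investigational product during TP1 and during TP2", measured as a proportion of subjects and not limited to serious events. Protocol Table 8 has the same endpoint, and Protocol 10.3.4.1 planned counts and percentages of AEs by relationship.

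**The planned tables.** SAP 11.2 covers any TEAE and then "serious TEAEs, TEAEs by severity, and serious TEAEs related to investigational product will be presented". It adds one separate summary, for treatment-related serious TEAEs. In SAP 11.4 the only relationship item is "Serious TEAEs related to Study Treatment".

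**What was dropped.** SAP Section 5 introduces a bullet list with "There will be no analysis of the endpoints below" and closes with "For other endpoints the statistical analysis was reduced as described in the sections of this SAP".

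**Missing relationship.** SAP 8.1.1 states the rule: "Subjects with the designation of treatment relationship for adverse events (AEs) and serious adverse events (SAEs) missing will have the worst case assumed". Section 11.2 says "Missing relationship to study treatment will be imputed as described in" Section 8.1.2, which deals with partial dates.

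**Windows.** SAP 8.2.3 ends the treatment-emergent class 30 days after product stop and calls later events post-treatment. SAP 8.3.2 counts Follow-up events as treatment-emergent. SAP 11.2 says "Treatment-emergent AEs (TEAEs) are defined as AEs reported at or after the start of the first infusion", with no end. SAP Section 11 assigns any event with onset on or after randomization to the double-blind period, also with no end.

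**The concern.** Non-serious related events count toward the Table 2 endpoint but not toward a serious-only table. Protocol 1.4 reports that injection site reactions and pain were the most common AEs in two Phase 3 studies of the subcutaneous product, and subjects here are dosed subcutaneously twice weekly. If such events are non-serious and judged related, they belong in the endpoint. Followed as written, the SAP would leave the report without a planned proportion for its only safety secondary endpoint, and without a statement that it was dropped.

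The window conflict bears on the same table. After the AE observation period, Protocol 9.4 requires an AE in the Responder Follow-up Period to be reported only if it is at least possibly related (9.6.2 has a corresponding rule for SAEs). An open-ended window would therefore add late events selected for being related.

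**Working it through.** No sample size, power or event count enters this point, so the check is a comparison of the text.

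**Is the endpoint dropped?** SAP Table 2 has 10 rows: 7 under objective 1, 1 under objective 2 and 2 under objective 3. The readable Section 5 bullets remove 4 of the 10: all-cause allograft failure, time to that failure, eGFR change from End-of-TP1 to End-of-TP2, and eGFR rate of change. The readable bullets on plasmapheresis and trough IVIg are not Table 2 rows. None is the related-AE endpoint. Some bullets are redacted, and nothing is inferred from them. Where later sections withdraw an analysis, they say so (10.2, 10.3, 10.6, 10.7); 11.2 and 11.4 make no such statement.

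**Is the endpoint produced?** It needs one proportion for TP1 and one per arm for TP2: 1 + 2 = 3. Take a non-serious TP2 event judged related. Under 11.2 it enters the any-TEAE, severity, and SOC/PT tables. It enters neither relationship summary in 11.2 nor the one in 11.4, because all three are restricted to serious events. Proportions planned: 0 of 3.

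**Do the windows agree?** Take an AE with onset 31 days after the last TP2 dose, in a subject with no Retreatment.

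| SAP section | Rule | Class of this event |
|---|---|---|
| 8.2.3 | ends 30 days after product stop; 31 > 30 | post-treatment |
| 8.3.1 with 8.3.2 | after last TP2 dose + 30 days is Follow-up; Follow-up counts as treatment-emergent | treatment-emergent |
| 8.1.2 (partial start dates) | compared with first dose only, no upper limit | treatment-emergent |
| 11.2 | at or after first infusion, no upper limit | treatment-emergent |
| 11 | onset on or after randomization, no end | double-blind period |

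One event thus gets two incompatible labels. Under the last two rows it also enters the TP2 by-arm tables. An event during Retreatment does the same, although 8.3.1 gives Retreatment its own on-therapy span and 11.1 summarizes Retreatment exposure separately.

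**The case against.** The best defence is that the reduction was deliberate. The study was terminated with 13 subjects randomized, Section 5 says other analyses were reduced as its sections describe, and the serious-only wording appears three times (twice in 11.2, once in 11.4). This may be so, and the documents do not settle intent. What stands against it is that no section says this endpoint is reduced, and SAP Section 3 undertakes to cover relevant secondary endpoints with available data. Relationship is assessed for every AE (Protocol 9.3).

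Several stronger readings that a reader might infer are not supported:

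- *That Table 2 proves the endpoint was retained.* It still lists four endpoints that Section 5 removes.
- *That the information is lost.* All AEs are listed, so the proportion could be derived by hand. Section 11.2 also counts TEAEs with missing relationship, in wording not clearly limited to serious events. Neither is a planned summary of the endpoint.
- *That 11.2 sets a competing rule based on report date.* Sections 8.1.2 and 11 work from start or onset dates, so its wording on reporting is better read as loose.
- *That non-randomized subjects have no end to their window.* Section 8.2.3 gives one: product stop + 30 days.
- *That the 8.3.1 periods are left unapplied.* That section says AEs are assigned to its periods. The difficulty is that Section 11 splits events differently and without an end.

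**Conclusion.** The point holds as a reporting and consistency defect. As written, the SAP plans none of the three proportions that its only safety secondary endpoint calls for, and does not say that the endpoint was dropped. The reference to 8.1.2 for missing relationship is a plain error. The TEAE definitions conflict for events more than 30 days after product stop, and Section 11 lets Follow-up and Retreatment events into the TP2 by-arm tables.

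No formal test is affected, since the SAP plans none. The numerical effect cannot be determined: the documents give no count of related, non-serious or late events, and neither the arm split of the 13 randomized subjects nor the size of the RiS set. A reader might infer that related events are being concealed, or that the safety comparison is biased toward one arm; nothing in the documents supports either inference. The conclusion rests on the readable Section 5 bullets only.

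**What to change.** 1. In SAP 11.2, add the number and percentage of subjects with any related TEAE, for TP1 on the RiS set and for TP2 by arm on the RWS set. Apply the 8.1.1 rule for missing relationship, and correct the cross-reference from 8.1.2 to 8.1.1. If a listing alone was intended, Section 5 should name the endpoint and say so; the table is preferable because the data exist.

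2. Use one onset-based TEAE definition in 8.1.2, 8.2.3, 8.3.2, 11 and 11.2: the 8.2.3 window, from first open-label dose to last dose + 30 days, with Retreatment handled as on-therapy as in 8.3.1.

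3. Keep the randomization-date split in Section 11. End the TP2 by-arm window at the earlier of last TP2 dose + 30 days or first Retreatment dose.

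4. Show later events as post-treatment in listings, not as TEAEs. Section 11.4 already has a listing for serious non-TEAEs. The whole-study summary that Section 11 extends to follow-up should use the same TEAE definition.

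The cost is one extra table, one corrected reference and edits to five sections. No new data are needed. TEAE counts may be slightly lower than under the open-ended rule.

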11.3 Adverse Events of Special Interest (AESI)

Adverse events of special interest of Treatment Period 2 will be presented for the RWS Analysis Set. In addition, adverse events of special interest will be summarized for C1-INH over the whole study for RWS Analysis Set and a summary across the whole study will be given for the RiS Analysis Set.

- Thromboembolic events
 - Systemic thrombotic or thromboembolic events not including catheter or dialysis related clots are of interest. Identification will be based on the Standardized MedDRA Query (SMQ) Embolic and thrombotic events (narrow),
- Anaphylaxis
 - Anaphylaxis will be identified using the SMQ - Anaphylactic reaction (broad).

Treatment-emergent adverse events of special interest will be summarized by SOC and PT.

A separate by-subject listing will be produced for all treatment-emergent adverse events of special interest based on RiS Analysis Set. A listing of terms included in each SMQ can be found in [Section 16.1](#) and [16.2](#).

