3.7 Study Oversight

3.7.1 Data Monitoring Committee(s)

The independent data monitoring committee (IDMC) is an independent expert advisory group consisting of medically qualified transplant nephrologists or surgeons with appropriate expertise in subjects with AMR, kidney transplant recipients, and/or evaluation of AEs and laboratory results relevant for detecting any possible safety issues, and a statistician. The IDMC is being utilized to provide an independent evaluation of the study at regular intervals with regard to the progress of the study and the safety data, namely for the incidence, frequency and nature of AEs, and in particular for TEEs. In particular, any systemic TEE, not associated with dialysis access or other vascular access devices, reported as related to the administration of investigational product by the investigator, will be reviewed ad hoc by the IDMC. The IDMC will adjudicate the causality assessment for the TEE based on the unblinded case report. In addition, the IDMC will review the primary efficacy endpoint data only at the planned interim analysis. Other data (eg, PK) may also be reviewed, as appropriate. Unblinding of data and provision of unblinded data to the IDMC will be performed by an independent statistical data analysis center that is not associated in any other way with the study. After this review, recommendations will be issued to CSL Behring (CSL) regarding the continuation of the study, eventual need for protocol modifications, or study termination.

The analysis plan for all IDMC data reviews will be outlined in the IDMC charter. The composition, activities, and responsibilities of the IDMC will also be described in the IDMC charter.

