4.1.2 Exclusion Criteria

Subjects must not be enrolled into the study if they meet any of the following exclusion criteria:

1. Recipient of an en bloc kidney transplant.
2. Ongoing dialysis > 2 weeks at Screening.
3. Hepatobiliary disease as indicated by 1 of the following:
 - a. Viral hepatitis ie, positive for HCV or HBV confirmed by nucleic acid testing (if positive, subjects must be receiving or have received antiviral therapy and have no history of cirrhosis), OR
 - b. Alanine aminotransferase > 3 times upper limit of normal, OR
 - c. Total bilirubin > 1.5 times upper limit of normal.
4. History of human immunodeficiency virus with acquired immunodeficiency syndrome at Screening.

5. Active bacterial or fungal infection that is clinically significant in the opinion of the investigator.
6. Not otherwise explained thrombotic microangiopathy on pre-enrollment kidney biopsy.
7. Known congenital bleeding or coagulopathy disorder.
8. Evidence of non-catheter or non-dialysis access-related deep vein thrombosis, stroke, myocardial infarction, or arterial embolus within the 3 months before the Day 1 Visit; catheter-related thrombosis or history of clotting a dialysis access is NOT exclusionary, unless a hereditary coagulopathy has been diagnosed.
9. Treatment with a complement inhibitor (eg, Soliris [eculizumab], Berlinert [C1-INH], Cinryze [C1-INH]), or experimental therapies for the treatment of AMR other than IVIg or rituximab (eg, bortezomib) within 14 days before administration of C1-INH at the Day 1 Visit.
10. Current cancer or a history of cancer within 2 years before providing informed consent, with the exception of successfully treated non-metastatic basal or squamous cell carcinoma of the skin, in situ breast or other in situ lesions considered cured by therapy.
11. Any medical condition that, in the opinion of the investigator, might interfere with the subject participation in the study, poses an added risk to the subject, or confounds the assessment of the subject.
12. Female subjects who are pregnant (as evidenced by a positive serum pregnancy test for choriongonadotropin beta at Screening) or breast feeding.
13. Female subject of childbearing potential or male subject not using or not willing to use a medically reliable method of contraception from the first dose of investigational product in any treatment period until 1 month after the last dose of investigational product in the same treatment period.

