9.1.2 Adverse Event of Special Interest

There are several AEs that will be monitored as AEs of special interest to enable an adequate risk-benefit evaluation of the C1-INH.

The following events will be considered AEs of special interest:

- Thromboembolic events (TEEs).
 - Any systemic TEE is considered an SAE and should be reported as such. Additionally, any non-systemic TEE (eg, a TEE associated with dialysis access or other vascular access) that meets the serious criteria must be reported as an SAE.
 - Any non-serious access-related thrombosis should be entered as an AE on the eCRF and will be part of the regular review of AEs of special interest by the IDMC.
- Anaphylaxis.
 - All events of anaphylaxis are considered SAEs and should be reported as such.

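### SAP 11.3 rules catheter and dialysis clots out of the thromboembolic AESI, but the query it uses brings them back in, and protocol 9.1.2 treats them as part of the AESI

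*SAP*

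**What the plan says.** SAP 11.3 defines the thromboembolic AESI in two adjacent sentences. The first sets the scope: "Systemic thrombotic or thromboembolic events not including catheter or dialysis related clots are of interest". The second gives the means: "Identification will be based on the Standardized MedDRA Query (SMQ) Embolic and thrombotic events (narrow", with the terms printed in SAP 16.1. On output, "Treatment-emergent adverse events of special interest will be summarized by SOC and PT", and a by-subject AESI listing is added.

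Protocol 9.1.2 says that certain events will be "monitored as AEs of special interest to enable an adequate risk-benefit evaluation of the C1-INH", and thromboembolic events (TEEs) are the first category it names. Under that heading it deals with three kinds of event:

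- systemic TEEs;
- "any non-systemic TEE (eg, a TEE associated with dialysis access or other vascular access", where it is serious;
- non-serious access-related thrombosis, which "will be part of the regular review of AEs of special interest by the IDMC".

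The protocol sets access events aside in another context. Section 3.7.1 limits ad hoc review by the data monitoring committee (IDMC) to "any systemic TEE, not associated with dialysis access or other vascular access devices" that the investigator reports as related to investigational product. Section 3.8 uses the same limit for the procedure that follows in the individual subject.

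**The concern.** The SAP's scope sentence and its identification rule give different sets of events, and nothing says how to get from one to the other. Two programmers could follow SAP 11.3 and produce different AESI tables. If the exclusion is applied, the table also leaves out events that the protocol places in the AESI.

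Thromboembolism is a named product risk in protocol 1.4. Access clots are plausible in this population: under exclusion criterion 8, "catheter-related thrombosis or history of clotting a dialysis access is NOT exclusionary" unless a hereditary coagulopathy has been diagnosed. What is at stake is whether the AESI summary means the same thing in the SAP, the protocol and the study report.

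**Working it through.** The plan states no figure to reproduce. The check compares texts and counts terms.

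**1. Terms printed in SAP 16.1**

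| Sub-list | Terms |
|---|---|
| Arterial | 138 |
| Venous | 93 |
| Unspecified or mixed vessel type | 150 |
| Total | 138 + 93 + 150 = 381 |

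**2. Terms that themselves name an access or catheter clot or occlusion.** There are five: arteriovenous fistula occlusion, arteriovenous fistula thrombosis, arteriovenous graft thrombosis, catheter site thrombosis and vascular access site thrombosis. 5 / 381 = 1.3%.

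**3. Terms that do not show whether the event is access-related.** There are at least ten:

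- shunt occlusion and shunt thrombosis (2);
- device occlusion, device related thrombosis, thrombosis in device, medical device site thrombosis and vascular device occlusion (5);
- graft thrombosis, vascular graft occlusion and vascular graft thrombosis (3).

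In a kidney transplant trial, graft thrombosis could be a clot in the allograft or in a dialysis graft. Together with step 2 this makes 5 + 10 = 15 terms, and 15 / 381 = 3.9%. All 15 are in the mixed list. Central-vein terms in the venous list, such as jugular vein thrombosis, raise the same question and are not in this count.

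**4. Is there an exclusion step?** All 15 terms are printed as narrow scope, and none is marked for removal. SAP 11.3 gives no list of deleted terms, case review, adjudication flag or eCRF field, and SAP sections 5, 7, 8 and 11 supply none. The five terms in step 2 can be removed by reading them. The ten in step 3 cannot.

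**5. The two ways of carrying out SAP 11.3**

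| Reading | Access or catheter clots | Conflicts with |
|---|---|---|
| Run the query as printed | Counted | The scope sentence in SAP 11.3 |
| Apply the exclusion | Left out, by an unstated method for unclear terms | Protocol 9.1.2 |

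SAP section 5, which lists changes from the protocol, does not mention a narrower AESI.

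**6. Effect on counts.** The documents give no adverse event counts, so the change in AESI counts cannot be computed. For scale only: SAP section 3 reports 13 randomized subjects, so one subject moved in or out is 1 / 13 = 7.7% of them.

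**The case against.** The strongest reply has four parts.

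**The two SAP sentences can be read together.** The query finds candidates and the scope sentence restricts them, so the gap is an unwritten step and not a contradiction. This is a fair reading of intent. It settles the five self-naming terms but gives no rule for the ten unclear ones, and it leads directly to the conflict with the protocol.

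**The protocol conflict is inferred.** The items under the TEE heading in 9.1.2 are reporting rules, and no single sentence says that access clots are AESIs. It is true that no such sentence exists. But 9.1.2 makes TEEs an AESI without limiting them to systemic events, and its own wording calls an access-related clot a non-systemic TEE. It also puts non-serious access thrombosis into the IDMC's AESI review. The inference is strong.

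**Seriousness could do the sorting.** Protocol 9.1.2 makes every systemic TEE a serious event, so a non-serious hit would not be systemic. This would help with some records, but neither document states it as a sorting rule, and serious access events would remain unresolved.

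**The consequence is very small.** This stands. Criterion 2 excludes subjects on dialysis for more than 2 weeks at Screening, and a permitted history says nothing about how often such clots occur on study. The trial was terminated, SAP 7.3 plans no formal testing, and SAP 11.2 lists all adverse events. The percentages of terms show where the ambiguity lies, not how large its effect is, and the group of ten is a minimum.

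**Conclusion.** The concern holds, at minor severity. SAP 11.3 excludes catheter and dialysis clots, identifies events with a list that contains them, and states no way to reconcile the two. Either way of carrying it out conflicts with a stated rule, in the SAP itself or in protocol 9.1.2.

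Five terms (1.3%) are directly affected and at least ten more are ambiguous, 15 of 381 (3.9%) in all. The effect on event counts is unknown. No event is hidden, because AESIs are shown by SOC and PT with a by-subject listing, and SAP 11.2 and 11.4 report treatment-emergent and serious events separately.

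The conclusion rests on the term list as printed in SAP 16.1, and on reading the items under the TEE heading of protocol 9.1.2 as part of that AESI category.

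**What to change.** Align SAP 11.3 with protocol 9.1.2 and tabulate thromboembolic AESIs in two rows: systemic, and access/catheter-related.

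- Assign the five self-naming terms to the access/catheter row by a list fixed in the SAP.
- Where the term does not show the relation (shunt, device, graft and central-vein terms), assign the record from the reported adverse event detail.
- Record each assignment before the study is unblinded, and show the row in the by-subject AESI listing. This protects the Treatment Period 2 comparison only, since Treatment Period 1 is open-label; there the gain is a documented rule.

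The cost is a change of SAP wording, one term flag in programming, one more table row, and a short documented review of the few unclear records. Both documents are satisfied and no event leaves the AESI output.
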